#### 10.5.4.2 Blood Donation

Subjects will be advised that they should not donate blood or loss of greater than 500 mL of blood within the previous 3 months or more than 100 mL within 30 days prior to signature of informed consent.

### 10.5.5 Removal of Subjects from Therapy or Assessment

Each subject will be informed of their right to withdraw from the study at any time and for any reason.

An Investigator will withdraw a subject from the study at any time for any of the following reasons:

- If a subject experiences a serious or intolerable AE, that prevents them from continuing.
- If a subject incurs a significant protocol violation which impacts on their safety or the scientific integrity of the study (this will be discussed on a case-by-case basis with the Sponsor).
- At the request of the Sponsor.

DNDi RD 777/34920 DNDi- 0690- 02

Final V3.0/ Date 07 December 2020

Confidential

Page 60 of 109

- If it is considered that the subject's health is compromised by remaining in the study or the subject is not sufficiently cooperative.
- If a subject is lost to follow-up.

The reasons for any subject withdrawal will be recorded on the study completion form of the case report form (CRF).

If a subject is withdrawn or chooses to withdraw from the study for any reason every possible effort will be made to perform the evaluations described for the post-study follow-up (see Table 6, Table 7 and Table 8). The data collected from withdrawn subjects will be included in the study report.

In the event of any abnormalities considered to be clinically significant, subjects will be followed up with appropriate medical management until values are considered to be clinically acceptable. Referral or collaborative care will be organised if considered necessary.

Fifty-four (54) subjects are required to complete the study. Subjects who withdraw from the study before receiving any IMP will be replaced. Subjects who are withdrawn from the study due to significant drug-related AEs will not be replaced. Replacement of all other subjects withdrawn from the study after receiving IMP will be decided on a case-by-case basis by the PI (or deputy) and Sponsor.

# 10.6 Investigational Medicinal Product

#### **10.6.1 Identity**

The identity of each IMP is detailed in Table 5

**Table 5** Identity of Investigational Medicinal Products

IMP Name	Strength	Presentation/Form	Route
DNDI-0690	100 or 200 mg of DNDI-0690	hard gelatine capsules	Oral
Matching Placebo	N/A	hard gelatine capsules	Oral

**Non-IMP** (**NIMP**): Iohexol solution (300mg/mL iodine).

### 10.6.2 Receipt and Storage

The IMP (DNDI-0690 and matching placebo) will be supplied by the Sponsor.

The investigational product will be supplied as hard gelatine capsules in HDPE bottles with induction seal closures. Each capsule contains either 100 mg or 200 mg of DNDI-0690. Each dose strength is presented as a Swedish orange, size 00 capsule. The investigational product also contains the following non-active ingredients: HPMC, SLS, sucrose, croscarmellose sodium and magnesium stearate.

A matching placebo formulation for all doses strengths is also provided. The placebo is made using the same non-active excipients as the investigational product (sucrose, croscarmellose sodium and magnesium stearate).

DNDi RD 777/34920 DNDi- 0690- 02

Final V3.0/ Date 07 December 2020

Confidential

Page 61 of 109

The Sponsor must notify the PI, or the Project Manager, prior to dispatch of IMP supplies, and of the anticipated date of their arrival. IMP should arrive at the study site at least 7 days before the first dosing day. The Sponsor shall address all supplies to:

### **The Production Manager**

The Pharmacy Simbec-Orion [name]

Upon receipt, supplies will be dealt with as per Simbec-Orion SOP SR-IMP 053. Temperature monitors included with shipments will be downloaded.

The IMPs will be stored in the original container under quarantine in a segregated, study-specific area, at or below 30°C in a secure, temperature-controlled pharmacy. The shipping documentation and bulk product qualified person (QP) certification will be reviewed. The supplies will subsequently be removed from quarantine and approved for use.

The NIMP, iohexol solution (300 mg/mL iodine) will be sourced by Simbec-Orion.

#### 10.6.3 Assembly and Release

The IMP will be assembled into unit doses by suitably trained Simbec-Orion staff according to the Simbec-Orion SOP SR-IMP 015.

The IMP will be labelled as specified in Annex 13 (manufacture of IMPs) of the European Commission guide to Good Manufacturing Practice (GMP).

The finished IMP will be certified by Simbec-Orion's QP according to the Simbec-Orion SOP SR-IMP 030.

#### 10.6.4 Administration

IMPs will be administered according to the following instruction:

- The IMPs will be administered fasted (after an overnight fast of at least 10 hours) with 240 mL water (more water will be provided if needed and the actual water taken with dose administration will be recorded in the eCRF). Subjects must remain upright for at least 4 h after dose, unless study procedures are performed.
- If a BID regimen is implemented, subjects will fast overnight for at least 10 hours (h) before each morning dose. The second, evening dose will be administered 10 hours following the morning dose. The second, evening dose shall be taken a minimum of 5 hours post mid-day meal, and one hour before the dinner. On Day 10, only a morning dose will be administered. (see section 10.5.3.1)
- A dose leader design will be implemented in **Part A and Part B** with 2 subjects being dosed on the first dosing day of EACH cohort. Of these 2, 1 will be on active drug and 1 on placebo. The remainder of the cohort will be dosed at least 48 hours later pending an acceptable safety profile in the dose-leader group and will contain 2 subjects on placebo and 5 subjects on active drug. This design allows maintenance of the "blind".

IMP administration will be documented in the CRF.

DNDi RD 777/34920 DNDi- 0690- 02

Final V3.0/ Date 07 December 2020

Confidential

Page 62 of 109

There will be at least 7 days between cohorts in Part A, and between Part A and Part B.

#### 10.6.5 Return/Destruction

All used IMP containers and unused IMP will be held under quarantine pending return/destruction.

The Sponsor must provide approval for return/destruction of all remaining IMP within 8 weeks after study completion, provided final drug reconciliation activities are fully completed. After this period, a charge for storage will be incurred.

All returns will be arranged at the earliest available delivery date. For IMP destruction, the Sponsor will receive the Certificate of Destruction 4 to 6 weeks from the date of removal from site.

### 10.6.6 Method of Assigning Subjects to Treatment Groups

Subjects will be allocated to treatment groups according to a randomisation code produced by Simbec-Orion using the PROC PLAN procedure of SAS® (the most up to date version will be used and this will be documented in the DMP). The randomisation code will include 2 dose-leaders (1 active:1 placebo) in each cohort in Part A and Part B.

Subjects will be numbered sequentially from 001 (*i.e.* 001, 002 etc.). Replacement subjects will be assigned the same randomisation as the subject they are replacing, however, 100 will be added to the number (*i.e.* 101 would replace 001 etc.).

### 10.6.7 Selection of Doses in the Study

The starting dose in Part A is once daily dose of 400 mg which was selected based the safety and PK data from the SAD study in human healthy volunteers. The rationale and justification of dose selection are detailed in Section 10.3.

### 10.6.8 Timing of Dose for Each Subject

OD doses will be administered at approximately 9.00 a.m. Subjects will be required to fast for at least 10 h overnight prior to each morning dose. The fast will be broken 4 h after dosing with a light lunch (see Section 10.5.3).

If a BID regimen is implemented, subjects will fast overnight for at least 10 hours (h) before each morning dose. The second, evening dose will be administered 10 hours after the morning dose. The second, evening dose shall be taken a minimum of 5 hours post mid-day meal, and one hour before the dinner. On Day 10, only a morning dose will be administered.

Two (2) dose leaders (1 active:1 placebo) will be dosed first in each cohort in Part A and Part B. The remainder of the cohort will be dosed a minimum of 48 hours later pending an acceptable safety profile in the dose-leader group.

### **10.6.9 Blinding**

A designated individual from the IMP Management Department at Simbec-Orion will generate the randomisation code under the guidance of a statistician. All other site and Sponsor personnel involved in the study will be blinded with regard to the IMP being administered. The pharmacist (or designee) responsible for the preparation of subject doses and emergency code

DNDi RD 777/34920 DNDi- 0690- 02

Final V3.0/ Date 07 December 2020

Confidential

Page 63 of 109

break envelopes will not be blinded and a copy of the original randomisation code will be issued to the pharmacist (or designee) for this purpose.

The bioanalytical scientist (at SGS), will be provided with a copy of the randomisation code for the purposes of analysing samples. The bioanalytical scientist will provide the drug concentration data for interim analysis and dose escalation data review in a re-coded subject number format, presented by dose level, in order to maintain the blind of study personnel.

**Subject doses:** Once the randomisation code has been authorised as per Simbec-Orion SOPs, each subject dose will be packaged and labelled for individual subjects by designated individuals from the IMP Management Department at Simbec-Orion on behalf of the Sponsor. The QP checks that the active drug and placebo are indistinguishable as part of the QP certification process.

**Code break envelopes:** Once the randomisation code has been authorised as per Simbec-Orion SOPs, the pharmacist (or designee) will produce individual sealed code-break envelopes that contain the treatment allocation(s) for each subject. The envelopes will be stored in the restricted access pharmacy. A set of code break envelopes will also be provided to the person responsible for PV.

*Emergency unblinding:* Where the site requires emergency access to an individual subject code Simbec-Orion will break the blind via the code break envelopes stored in the pharmacy without prior consultation with the Sponsor. In such an event, the Sponsor will be notified as soon as possible via email.

*Non-emergency unblinding:* If an Investigator believes that knowledge of the IMPs received by a subject is essential for appropriate treatment of an AE, the code will be broken via the code break envelopes stored in the pharmacy. Where practical, the Investigator should ideally consult the Sponsor before breaking the code. In any event, Sponsor will be informed as soon as practical whenever the code has been broken for a subject.

If the blind needs to be broken for an individual subject, the date and reason will be recorded in the subject's CRF (the treatment allocation will not be captured in the CRF). Unless necessary, the Investigator will not reveal the unblinded treatment code to any other member of the clinical team involved in the study or to the Study Monitor. If the code is broken for any individual subject, the subject will be withdrawn from the study and the procedures accompanying withdrawal performed. If the code is broken without justification, this will be deemed a serious GCP breach.

### 10.6.10 Prior and Concomitant Therapy

#### 10.6.10.1 Prior Medication

Prescription or non-prescription drugs, including vitamins, herbal and dietary supplements should not be taken within 28 days (or 5 half-lives of the taken drug, whichever is longer) prior to the first dose of IMP, unless in the opinion of the Investigator and Sponsor's Responsible Physician the medication will not interfere with the study procedures or compromise subject safety. Prescription or non-prescription drugs, including vitamins, herbal and dietary supplements taken during the 28 days before the first dose of IMP, and the reason for taking them, will be noted in the subject's CRF.

DNDi RD 777/34920 DNDi- 0690- 02

Final V3.0/ Date 07 December 2020

Confidential

Page 64 of 109

Administration of up to 4 g of paracetamol per day within 7 days of IMP administration is allowed.

### 10.6.10.2 Concomitant Medication:

All drugs known to interfere with the renal transporters MATE1 and/or OCT2 shall be avoided (for example: cimetidine, ritonavir, trimethoprim, cisplatin) as they may create interferences in the assessment of the effect of DNDI-0690 on renal function.

Prescription or non-prescription drugs, including vitamins, herbal and dietary supplements should not be taken throughout the duration of the study, unless warranted by the treatment of AEs occurring after first IMP dose. In case of need for analgesia, paracetamol (which may be taken as an analgesic to a maximum of 2 g in 24 h) will be privileged, followed by ibuprofen (which may be taken as an analgesic to a maximum of 1.2 g in 24 h (400 mg 3 times a day)).

If intake of ANY prior or concomitant medication is necessary during the study, the daily dosage, duration and reasons for administration will be recorded on the subject's CRF.

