**DNDi** 

RD 777/34920

DNDi- 0690- 02

In conclusion, preclinical toxicology results indicate that the main target for toxicity of DNDI-0690 is the kidney. Potential renal toxicity can be closely monitored in clinical trials through standard laboratory examinations and specific renal parameters (creatinine, BUN, Cys C).

Due to heart changes as a consequence of nephrotoxicity were considered agonal in their nature and contributory to death together with renal changes, circulating levels of troponin I will continue to be monitored in the multiple ascending dose (MAD) study in healthy subjects at admission, at last day of treatment and in case of any ECG clinically significant abnormality during the course of treatment.

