#### 9.2 Part C

**Primary Objective:** To evaluate renal function (glomerular filtration rate (GFR)) before and after administration of DNDI-0690 in healthy subjects in fasted condition at maximum well tolerated dose tested in Part A or below.

Confidential

Final V3.0/ Date 07 December 2020

Page 47 of 109

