#### 10.3.3 Part C

In line with the FDA's draft guidance for industry (U.S. Department of Health and Human Services 2017), additional evidence from clinical mechanistic studies is required in order to confirm whether or not the elevations in serum creatinine observed in the SAD study are due

DNDi RD 777/34920 DNDi- 0690- 02

Final V3.0/ Date 07 December 2020

Confidential

Page 53 of 109

to inhibition of the MATE-1 or other transporters. To address this, once a maximum tolerated dose of DNDi-0690 will be identified or at the highest dose tested, a cohort to calculate measured glomerular filtration rate (mGFR) will be conducted. mGFR data will be used for assessment of renal function. In the mGFR cohort, 9 subjects will receive multiple doses of DNDI-0690 or placebo once daily in a similar study design to the Part A cohorts, with the following specificities:

- Dose in Part C will already have been explored, no sentinel group will be implemented in this cohort.
- All subjects will receive 5 mL of iohexol solution (300 mg/mL iodine) intravenously on Day -1, Day 10, and optionally Day 24-28 that will be flushed with 10 mL of normal saline solution. On Day -1, iohexol will be administered at the same time as expected dosing of study drug on Day 10. On Day 10, iohexol will be administered immediately after dosing of study drug.
- Precaution for use as per iohexol summary of product characteristics (SmPC) will be respected.

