- 17. Serious adverse reaction or clinically relevant hypersensitivity to any drug or the formulation excipients (Hypromellose [HPMC], sodium lauryl sulphate [SLS], sucrose, croscarmellose sodium and magnesium stearate).
- 18. Presence or history of clinically significant allergy requiring treatment (including asthma, urticaria, clinically significant allergic rash or other severe allergic diathesis), as judged by the Investigator. Hay fever is allowed unless it is active.

DNDi RD 777/34920 DNDi- 0690- 02

Final V3.0/ Date 07 December 2020

Confidential

Page 56 of 109

- 19. Donation or loss of greater than 500 mL of blood within the previous 3 months or more than 100 mL within 30 days prior to signature of informed consent.
- 20. Subjects who are taking, or have taken, any prescribed or over-the-counter drug (including anti-acid drugs) or vitamins/herbal remedies (*i.e.* St. John's Wort and others which are known to interfere with the CYP3A4 and P-gp metabolic pathways) or hormone replacement therapy (HRT) or any drug known to modify the MATE-1/OCT-2 renal transporters (such as, for example, cimetidine, ritonavir, trimethoprim, cisplatin) in the 28 days before IMP administration (or 5 half-lives of the taken drug, whichever is longer). Administration of up to 4 g of paracetamol per day within 7 days of IMP administration is allowed.
- 21. Surgery within 12 weeks prior to Screening, with the exception of appendectomy.
- 22. Any surgery (*i.e.* gastric bypass) or medical condition that may affect absorption of orally administered drugs.
- 23. Failure to satisfy the Investigator of fitness to participate for any other reason
- 24. Breastfeeding and lactating females.

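### Section 10.6.10.2 allows ibuprofen as second-line analgesic with no exception around the Part C iohexol tests, although GFR is Part C's only objective: minor and cheap to close

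*Protocol*

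**What the plan says.** Section 10.6.10.2 (Concomitant Medication) has two relevant rules. The first tells sites to avoid drugs acting on the MATE1 and OCT2 renal transporters, "as they may create interferences in the assessment of the effect of DNDI-0690 on renal function". The second forbids other medication during the study "unless warranted by the treatment of AEs occurring after first IMP dose". For pain it puts paracetamol first (up to 2 g in 24 h), "followed by ibuprofen (which may be taken as an analgesic to a maximum of 1.2 g in 24 h". Neither rule differs by study part or by day, and nothing elsewhere in the protocol restricts ibuprofen or NSAIDs. Any intake is recorded in the CRF with dosage, duration and reason.

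Section 9.2 gives Part C a single objective: "To evaluate renal function (glomerular filtration rate (GFR)) before and after administration of DNDI-0690 in healthy subjects". Section 10.3.3 explains why Part C is needed: "additional evidence from clinical mechanistic studies is required in order to confirm whether or not the elevations in serum creatinine" seen in the single-dose study come from transporter inhibition. GFR is measured by iohexol on Day -1, on Day 10 and optionally at follow-up (Day 24 to 28). The Synopsis gives 6 active and 3 placebo subjects for Part C.

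Medication before dosing is controlled more tightly. Exclusion criterion 20 (Section 10.4.2) rules out prescribed and over-the-counter drugs "in the 28 days before IMP administration (or 5 half-lives of the taken drug, whichever is longer", apart from limited paracetamol. Section 10.6.10.1 makes an exception only where the investigator and the sponsor's physician judge that "the medication will not interfere with the study procedures or compromise subject safety".

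**The concern.** The transporter ban mainly protects creatinine, because those drugs act on creatinine secretion. Section 10.3.1 describes iohexol as a marker filtered freely by the glomerulus, and it was chosen to avoid that problem. The section has no matching safeguard for filtration itself, which is what iohexol measures, and the one drug it names after paracetamol belongs to a class that may change filtration.

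Timing adds to this. The adverse-event exception opens only after the first dose, so the Day -1 baseline is largely protected and any ibuprofen would fall mainly on the Day 10 side of the comparison. Section 8.5.1 also states that "preclinical toxicology results indicate that the main target for toxicity of DNDI-0690 is the kidney", so renal findings in this study will be read closely. With so few subjects, one affected value carries visible weight in its arm.

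**Working it through.** The protocol has no figure to reproduce: Section 10.9.3 says the sample size rests on no formal calculation, and no SD for mGFR is given. The arithmetic below only gives scale.

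**Inputs from the protocol**
- Arm sizes in Part C: 6 active, 3 placebo (Synopsis, Part C, Day 10).
- Renal signal to be explained: an apparent 12 to 14% fall in creatinine-based GFR in the single-dose study (Section 8.6.1).
- Headache in that study: 3 fasted males on active, 8.3%, which implies 3/36 (Section 8.6.1).

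**Assumed inputs**
- One subject takes ibuprofen near Day 10 and that subject's mGFR falls by f = 10%, range 0 to 20%. Zero means no effect.
- The ordinary SD of within-subject change is s = 5 to 10 percentage points.

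**Shift of an arm mean** = -f/n
- Active user, n = 6: 0, -10/6 = -1.67, -20/6 = -3.33 for f = 0, 10, 20.
- Placebo user, n = 3: 0, -10/3 = -3.33, -20/3 = -6.67.

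**Shift of the active-minus-placebo contrast** = -f/6 for an active user, +f/3 for a placebo user. At f = 10 this is -1.67 or +3.33 points. The sign depends on the user's arm.

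**Against sampling error**: SE of the contrast = s × √(1/6 + 1/3) = 0.707 s, which is 3.54 points at s = 5 and 7.07 at s = 10.
- Active user, f = 10: 1.67/7.07 = 0.24 to 1.67/3.54 = 0.47 SE.
- Placebo user, f = 10: 3.33/7.07 = 0.47 to 3.33/3.54 = 0.94 SE.
- Extreme corner (placebo user, f = 20, s = 5): 6.67/3.54 = 1.89 SE. A 95% interval extends at least 1.96 SE either side, so even this shift stays within it.

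**Against the signal**: taking 13% as the midpoint, 1.67/13 = 0.13 for an active user and 3.33/13 = 0.26 for a placebo user, about one-eighth and one-quarter.

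**How often?** The protocol does not say. At the single-dose headache rate, the chance of at least one headache among 9 subjects is 1 - (33/36)^9 = 54%. This does not estimate ibuprofen use, which also requires that paracetamol proves insufficient and that the intake falls close to Day 10. The single-dose headaches were mild and resolved without treatment.

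**The case against.** The best case for leaving the text alone has four parts.

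*The rules do not conflict.* A reader might infer that the section contradicts itself. It does not. The transporter ban serves the specific question about creatinine secretion, and the section never claims to bar every drug with a possible renal effect. This stands: the point is a gap, not an inconsistency.

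*The causal step is external.* The protocol nowhere says that ibuprofen alters GFR, and the assumed range includes zero. This stands and keeps the priority low.

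*The damage is recoverable.* A reader might infer that a contaminated Day 10 value cannot be repaired. That goes too far. Intake is recorded, so the affected subject can be identified. Cystatin C and the GFR derived from it are assessed with the Day 10 laboratory tests (Table 8, footnote 4). A repeat iohexol test is possible at follow-up after an abnormal result. What remains is that setting the subject aside leaves 5 active or 2 placebo subjects, so prevention is better.

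*Existing safeguards are good.* Paracetamol comes first, subjects are resident under supervision until Day 12, and fluid intake is prescribed on iohexol days. A restriction for the whole dosing period that lapses whenever paracetamol is judged inadequate would nearly restate the present second-line rule. This stands too, and is why the change should be a short, firm window around the tests.

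**Conclusion.** The gap is real but minor. The analgesic rule leaves the Part C iohexol measurement open to a drug that may affect filtration, and closing it costs almost nothing. On the assumed 10% fall in one user, the contrast moves by 1.7 or 3.3 points, or 0.24 to 0.94 SE. Both the fall and the SD are assumptions.

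A reader might infer that Part C is biased against DNDI-0690. The documents do not support that. The rule is the same in both arms, and Section 8.6.1 reports adverse events in similar proportions on active and placebo in the single-dose study. An affected Day 10 value would lower its own arm's before-after change, but the comparison with placebo could move either way. Nor would one such value by itself reverse the conclusion of a comparison that Section 10.9.2.5.6 analyses descriptively with 95% confidence intervals. Priority: optional improvement.

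**What to change.** Add to Section 10.6.10.2:

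> In Part C, ibuprofen and other NSAIDs are not permitted from 48 h before iohexol dosing on Day 10 until the last iohexol sample, nor in the 48 h before and during any follow-up iohexol test; paracetamol is used instead. If an NSAID is medically unavoidable in this window, the subject's mGFR for that day is flagged and the mGFR summary is also shown without it.

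The 48 h is a proposed value for the sponsor to confirm. With sampling to 5 h after iohexol, the Day 10 window lasts 48 + 5 = 53 h, all while subjects are resident. The follow-up test comes after discharge, so subjects who may need it must be told of the restriction in advance. No new data collection is needed, because intake is already recorded. The downside is one fewer second-line analgesic for a few days in nine subjects, and the last sentence still allows treatment when it is needed.
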